#### **7.4.2.1.2 Infusion Interruptions/Re-Start/Dosage Adjustments due to Adverse Events**

##### **7.4.2.1.2.1 General Guidelines**

Subjects should be assessed for adverse events at each visit. The severity of the adverse event will be graded using the CTCAE version 5.0 ([Section 12.4](#)), with the exception of CRS, which must be graded using the criteria referenced in the publication by [Lee et al, 2014](#) (see [Table 7-3](#)) and TLS, which must be graded according to the Cairo Bishop criteria referenced in the publication by [Coiffier et al, 2008](#) (see [Section 12.12](#)).

Infusion modification and dose reduction due to an adverse event will be performed according to the instructions described below and outlined in [Table 7-1](#) and [Table 7-3](#).

Infusion interruptions for other reasons need to be discussed with the Amgen medical monitor.

If infusion interruptions of < 14 days occur within a cycle the cycle will be resumed. The counting of the cycle days will not be stopped with an infusion interruption (eg, if the infusion is stopped on cycle day 5 and resumed 5 days later, the day of re-start is cycle day 10).

Following an infusion interruption with < 7 days remaining for infusion after resumption of the cycle, the last treatment days can be skipped and treatment will be continued with the next cycle after a 2-week infusion free interval.

However, treatment should not be given for < 14 days per cycle. An infusion interruption of more than 2 weeks or several interruptions exceeding a total of 14 days of treatment per cycle due to serious adverse events/adverse events require permanent treatment discontinuation.

Please note: the guidance in [Section 7.4.2.1.2](#) does not apply to the treatment holiday described in [Section 7.1.1.2](#).

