#### Delay of Subsequent Infusion due to Adverse Events

Events occurring after the end of the infusion and requiring a delay of treatment will be managed by delay of the subsequent infusion. The site should record any delay of an infusion on the eCRF and provide the start and stop date/time of the infusion.

Events requiring a delay of the subsequent infusion are listed in [Table 7-1](#). Infusion interruptions or delays **greater than 7 days** for other reasons need to be discussed with the Amgen Medical Monitor. **Delays of treatment cycles beyond 14 days are not permitted.**

Events requiring an infusion interruption including guidance for management, re-start, and permanent discontinuation are listed in [Table 7-1](#) and [Table 7-3](#).

---

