**Table 7-1. Infusion Interruptions/Permanent Discontinuations and Management of Adverse Events Including Dose Reductions**

	Interruption	Specific Management	Re-Start Guidance	Permanent Discontinuation
Tumor Lysis Syndrome (TLS) – Grading according to Cairo-Bishop Criteria				
Grade 2 - 3	Immediate interruption until event has improved to grade $\leq 1$	TLS prevention and management as per local standard of care and institutional guidelines.	
 
• Re-start possible if successfully managed and improvement to grade <math>\leq 1</math> in <math>\leq 14</math> days
 
• Hospitalization: Minimum 48 hours for start of next infusion
 
• Dose modification: reduce to next lower dose (ie, 200 <math>\mu\text{g}/\text{day}</math> for subjects originally receiving 400 <math>\mu\text{g}/\text{day}</math> or 400 <math>\mu\text{g}/\text{day}</math> for those originally receiving 600 <math>\mu\text{g}/\text{day}</math>) or if dose escalation is desired consult with Amgen medical monitor.
 
 
Additional measures: additional assessments and TLS premedication prior to infusion restart and next cycle infusion as per institutional standards  Sections 7.4.2.1.2.3/7.4.2.1.2.4
	
If symptoms/signs do not resolve in <math>\leq 14</math> days, consult with Amgen medical monitor if restarting treatment is desired.
 
In case of appearance of same event at grade 3 or higher.

Grade 4	Immediate interruption	As for grade 3 TLS	
 
• Do not restart
 
	Permanent discontinuation

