b High dose vasopressors (all doses are required for  $\geq 3$  hours): norepinephrine monotherapy  $\geq 20 \mu\text{g}/\text{min}$ , dopamine monotherapy  $\geq 10 \mu\text{g}/\text{kg}/\text{min}$ , phenylephrine monotherapy  $\geq 200 \mu\text{g}/\text{min}$ , epinephrine monotherapy  $\geq 10 \mu\text{g}/\text{min}$ ; if on vasopressin, vasopressin + norepinephrine equivalent of  $\geq 10 \mu\text{g}/\text{min}$ ; if on combination vasopressors (not vasopressin), norepinephrine equivalent of  $\geq 20 \mu\text{g}/\text{min}$ .

c All sites will ensure that CRS rescue medications are available on-site, including corticosteroids and (for sites in regions where tocilizumab is approved and available, eg, the US and Germany) 2 doses of tocilizumab per study subject.

#### 7.4.2.1.3 Permanent Discontinuation of AMG 420

AMG 420 treatment will be permanently discontinued in the event of:

- infusion-related reaction grade 4 (the infusion has to be stopped immediately)
- grade 4 CRS
- grade 2 or 3 CRS meeting any of the criteria listed below:
  - grade 2 or 3 CRS that does not improve to  $\leq$  grade 1 within 7 days
  - grade 3 CRS that does not improve to  $\leq$  grade 2 within 5 days
  - if a subject experiences 2 separate grade 3 CRS events
  - if a subject experiences repeat grade 2 CRS event after dose reduction
  - grade 3 CRS at the initial run-in dose of the first treatment cycle if a dose step is being used
- grade 3 or higher TLS
- neurologic events considered related to AMG 420 by the investigator and meeting one or more of the following criteria:
  - grade 3 neurologic event leading to treatment interruption and has not resolved to  $\leq$  grade 1 within 14 days despite infusion interruption
  - grade 3 neurologic event that recurs after dose reduction
  - grade 4 neurologic event
- DLT or other unmanageable toxicity unless a subject has a clear clinical benefit from treatment, the toxicity has resolved to  $\leq$  grade 1 or baseline and after consultation with the sponsor
- in case of re-appearance of the same grade 4 adverse event
- treatment interruption of more than 2 weeks or several interruptions exceeding a total of 14 days of treatment per cycle due to serious adverse events/adverse events
- possible DILI requiring permanent withholding as per [Section 7.4.3](#)
- non-manageable GvHD
- subjects who require more than 1 dose reduction
- disease progression as defined by revised IMWG response criteria

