### 7.8.2.7 Tumor Lysis Syndrome

Tumor Lysis Syndrome is a severe, life-threatening disorder that typically occurs in highly proliferative malignancies. Tumor Lysis Syndrome is frequently observed in patients with hematologic malignancies such as ALL and Burkitt's lymphoma. Tumor Lysis Syndrome is rarely reported in patients with multiple myeloma although patients with a high tumor burden may be at greater risk for TLS ([Chang et al, 2011](#); [Cairo et al, 2010](#)). However, given effective new treatments are now available TLS incidence has been reported to be  $\leq 5\%$  in patients with multiple myeloma who received different treatments ([Howard et al, 2016](#)). Tumor Lysis Syndrome is characterized by a group of metabolic disorders caused by the massive and abrupt release of cellular metabolites into the blood including lactate dehydrogenase (LDH), uric acid, phosphorus, potassium, and calcium after lysis of the malignant cells ([Coiffier et al, 2008](#)). The metabolic complications predispose patients with cancer to various clinical complications included renal failure, seizures, cardiac arrhythmias, and even sudden death. To allow for early diagnosis all subjects must be monitored closely for laboratory and clinical evidence of a possible TLS as outlined in [Section 12.12](#) of the protocol.

To prevent TLS, ensure all subjects are well hydrated and provided supportive care measures before administration of AMG 420 as detailed in [Section 7.8.2.1](#). Monitor for evidence of TLS during treatment and manage promptly including interruption of AMG 420 infusion as outlined in [Table 7-1](#). Subjects who experience TLS should be managed according to the local standard of care and institutional guidelines. Supportive therapy, including rasburicase, may be used as clinically indicated at the investigator's discretion.

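### Grade 3 tumor lysis syndrome is a permanent stop in Protocol 7.4.2.1.3 but sits in a restart row of Table 7-1; the 14-day stop likewise lacks exceptions for rows that allow later restart

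*Protocol*

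**What the plan says.** **TLS.** Protocol 7.4.2.1.3 gives the events after which AMG 420 is permanently discontinued. One bullet is "grade 3 or higher TLS". The only bullet with an 'unless' clause is the one on dose-limiting toxicity (DLT) or unmanageable toxicity.

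Table 7-1 has one TLS row for grades 2 and 3 and a separate row for grade 4. In the grade 2 to 3 row, the restart column reads "Re-start possible if successfully managed and improvement to grade" 1 or less in at most 14 days, at the next lower dose. The permanent-discontinuation column has two entries. For an event unresolved at 14 days the instruction is "consult with Amgen medical monitor if restarting treatment is desired". The other entry is "In case of appearance of same event at grade 3 or higher". The instruction not to restart appears only in the grade 4 row.

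Two sections send sites to this table. Section 7.8.2.7 tells them to "manage promptly including interruption of AMG 420 infusion as outlined in" Table 7-1. Section 7.4.2.1.2.2 states: "Events requiring an infusion interruption including guidance for management, re-start, and permanent discontinuation are listed in" Tables 7-1 and 7-3.

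**14-day stop.** Section 7.4.2.1.2.1 requires permanent discontinuation after "An infusion interruption of more than 2 weeks or several interruptions exceeding a total of 14 days of treatment per cycle" when adverse events are the cause, and 7.4.2.1.3 repeats this. The only exception in 7.4.2.1.2.1 is the treatment holiday. The same section adds that "treatment should not be given for < 14 days per cycle". Sections 7.4.2.1.2.2 and 9.1.2 also forbid delaying a cycle by more than 14 days.

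Table 7-1 lets neurotoxicity restart up to day 28 if the medical monitor approves. Table 7-2 requires symptomatic COVID-19 to be held until at least 10 days after acute symptoms fully resolve. Both of its COVID-19 rows set a conditional stop beyond 28 days.

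**The concern.** The two TLS instructions name the same event and the same grade and give opposite answers. The usual rule that a specific provision overrides a general one therefore cannot choose between them. A site that follows the table it is sent to could restart a subject who must stop under 7.4.2.1.3.

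The 14-day stop has the same kind of gap. Read literally, it ends treatment for subjects whom Tables 7-1 and 7-2 would allow to resume, and no sentence says which text controls.

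Subject safety is the first stake. The second is consistent reporting: adverse events leading to interruption or withdrawal (SAP 9.6.2), reason for ending treatment (SAP 9.2) and exposure (SAP 9.6.8) all depend on which instruction a site followed, in a study of about 20 subjects.

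**Working it through.** There is no sample size, power or error rate to reproduce. The check compares the passages and counts days.

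**Step 1. TLS rules side by side**

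| Grade | 7.4.2.1.3 | Table 7-1 |
|---|---|---|
| 2 | not listed | restart possible at lower dose |
| 3 | permanent stop | in the same restart row as grade 2 |
| 4 | permanent stop | do not restart |

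Only grade 3 disagrees. The stop cell on grade 3 or higher has two readings:
- *Recurrence at grade 3.* A first grade 3 event may then restart, which contradicts 7.4.2.1.3.
- *First appearance at grade 3.* This agrees with 7.4.2.1.3, but the row's restart guidance for grade 3 then has nothing to apply to.

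Neither reading leaves a consistent text.

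**Step 2. How often it could matter**
- Section 7.8.2.7 cites a TLS incidence of at most 5% in myeloma across treatments. In 20 subjects that is 20 × 0.05 = 1 expected case at most, of any grade. The documents give no grade 3 figure.
- The drug-related serious events listed for the 35 first-in-human subjects (Protocol 3.2.2.4) include no TLS.
- Appendix 12 ties laboratory TLS to the period from 3 days before to 7 days after the start of treatment, and clinical TLS requires laboratory TLS. If that start means the first infusion, the event falls inside the 4-week DLT window of 7.4.1. A grade 3 event there would usually be a DLT.

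**Step 3. Neurotoxicity**

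Table 7-1 and 7.4.2.1.3 agree on two stops: grade 4, and grade 3 not resolved to grade 1 or less within 14 days. The day-28 allowance therefore matters for a rise from grade 0 to 2, or for a grade 3 event that resolved in time but restarted late. For both, the blanket 14-day stop says the opposite.

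**Step 4. COVID-19 day count**

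Inputs: s = days from symptom onset to complete resolution; minimum hold after resolution = 10 days (Table 7-2); infusion days 1 to 28; next cycle starts on day 43 (Table 2-1 footnote). Assumption: the infusion stops at symptom onset.
- Minimum hold h = s + 10.
- s = 4: h = 14, not more than 14.
- s = 5: h = 15, more than 14.
- If the 15 days lie wholly within the infusion period (onset on days 1 to 14), 28 − 15 = 13 infusion days are given. That also falls below the 14-day minimum per cycle.
- Onset in the infusion-free interval, for example day 42 with s = 6: h = 16, earliest start day 42 + 16 = 58, delay 58 − 43 = 15 days. This exceeds the 14-day cycle-delay limit.
- Asymptomatic infection sets a minimum hold of only 10 days, so it forces no conflict.

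**The case against.** **Sponsor involvement.** A reader might infer that a site can restart after grade 3 TLS within 14 days with no outside check. The row itself does ask for the medical monitor only when dose escalation is wanted or 14 days have passed. But most TLS as defined in Appendix 12 would be a cycle 1 DLT, and the DLT bullet in 7.4.2.1.3 allows continuation only with clear benefit, resolution and sponsor consultation. This narrows the gap considerably. It does not close it: the TLS bullet has no such exception, and if the start of treatment is read per cycle, later cycles lie outside the DLT window.

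**Wording of the stop cell.** Table 7-2 speaks of reappearance when it means recurrence, while the TLS cell speaks of appearance. That favors the first-appearance reading, under which the table already agrees with 7.4.2.1.3. The point is fair, but the reference to the same event keeps recurrence arguable, and the row still offers grade 3 a restart.

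**TLS beyond 14 days.** A reader might infer that Table 7-1 permits restart here. It does not. The text is an invitation to consult, placed in the stop column.

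**Mandatory against permissive.** Section 7.4.2.1.3 is mandatory and the tables only permit. Stopping therefore complies everywhere, and a careful site would stop.

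**The 14-day rule.** Late neurotoxicity restarts need medical monitor approval, and COVID-19 restarts need investigator and monitor agreement, so no site restarts alone. This stands as mitigation, but no text lets the monitor set the 14-day stop aside. In addition, 7.4.2.1.2.1 may mean calendar days rather than lost infusion days, so thresholds by onset day outside the infusion period should not be pressed against that stop.

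**Reach.** The Amendment 5 rationale refers to program termination and no further drug supply, and the number still on treatment is not given. SAP 9.6.2 also drops adverse event tables when two or fewer subjects have the event.

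**Conclusion.** The inconsistency is real and should be corrected. For grade 3 TLS, 7.4.2.1.3 and Table 7-1 give opposite instructions, and neither reading of the stop cell reconciles them. Secondarily, the 14-day stop contradicts the neurotoxicity and COVID-19 rows, and symptomatic COVID-19 of 5 or more days forces that conflict when the hold falls within the infusion period.

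The size is modest. At the incidence the protocol cites, at most about one TLS case of any grade would be expected in 20 subjects, and most would reach the sponsor as a DLT. A reader might infer that the DLT counts are affected; they are not, because a DLT is classified at the event and not by what is done afterwards. Disposition and exposure summaries could shift by a subject or so.

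This rests on three assumptions: the cited incidence applies to AMG 420, the start of treatment in Appendix 12 means the first infusion, and a COVID-19 hold begins at symptom onset.

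**What to change.** (a) In Table 7-1, limit the TLS restart row to grade 2 and move grade 3 into the row that forbids restart. If the sponsor intends grade 3 restart, change the 7.4.2.1.3 bullet to grade 4 or recurrent grade 3 TLS and make the stop cell say recurrence.

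(b) Add one exception to the 14-day stop (7.4.2.1.2.1 and 7.4.2.1.3), the 14-day cycle-delay limit (7.4.2.1.2.2 and 9.1.2) and the 14-day minimum per cycle (7.4.2.1.2.1). It should cover neurotoxicity as stated in Table 7-1, up to 28 days with medical monitor approval and with the grade 3 and 4 stops unchanged, and COVID-19 as stated in Table 7-2. The neurotoxicity exception should not be confined to events below grade 3, because that would remove a late restart that the row now permits for a grade 3 event resolved in time. For TLS unresolved at 14 days, either delete the consultation option or list it as an exception.

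(c) State that 7.4.2.1.3 controls wherever no exception is written.

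The cost is a wording amendment with IRB/IEC submission, because stopping rules change, plus a sponsor decision on the intent for grade 3 TLS. It adds no procedures, visits or subjects.

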#### **7.4.3 Hepatotoxicity Stopping and Rechallenge Rules**

Refer to [Section 12.7](#) for details regarding DILI injury guidelines, as specified in the Guidance for Industry Drug-Induced Liver Injury: Premarketing Clinical Evaluation, July 2009.

#### **7.5 Preparation/Handling/Storage/Accountability**

Guidance and information on preparation, handling, storage, accountability, destruction, or return of the investigational product, non-investigational product, or other protocol-required therapies during the study are provided in the IPIM.

#### **7.6 Treatment Compliance**

Compliance to treatment and the corresponding assessments should be followed according to the Schedule of Activities ([Section 2.2](#)) and the Treatment Procedures ([Section 7.1](#)). Refer to the IPIM for additional information.

#### **7.7 Treatment of Overdose**

The effects of overdose of this product are not known. The daily AMG 420 dose may be up to 10% lower or higher than specified in the protocol in order to account for possible pump inaccuracies. A dose of up to 10% higher than the intended dose may not require specific intervention.

In case of overdose of > 10% of planned dose, the infusion should be immediately stopped. Consultation with the Amgen medical monitor is required for prompt reporting of clinically apparent or laboratory adverse events possibly related to overdosage. Consultation with the Amgen medical monitor is also required even if there are no adverse events, in order to discuss further management of the subject. If the overdose

results in clinically apparent or symptomatic adverse events, the subject should be followed carefully until all signs of toxicity are resolved or returned to baseline and the adverse event(s) should be recorded/reported per [Section 9.2.3](#).

Resumption of AMG 420 infusion is possible after consultation with the Amgen medical monitor and should adhere to the guidelines in [Section 7.4.2](#).

A dose of >10% higher than the intended AMG 420 dose will be considered clinically important and classified as a serious adverse event under the criterion of “other medically important serious event” per [Section 12.4](#).

## **7.8 Prior and Concomitant Treatment**

### **7.8.1 Prior Treatment**

Prior therapies that were being taken/used from initial diagnosis of multiple myeloma through the start of screening will be collected.

For prior therapies being taken for multiple myeloma, the therapy line, name of therapeutic agent, regimen, type of therapy, start date, and stop date will be collected, as well as best responses.

For radiotherapy the name, site, start date, and stop date will be collected.

For prior autologous or allogeneic HSCT, hematopoietic stem cell mobilization source, conditioning regimen, number of cells infused ( $CD34^+$ /kg) on day 0, date of neutrophil engraftment (first day that  $ANC > 0.5 \times 10^9/L$  for 3 consecutive days), date of platelet engraftment (first day that platelets  $> 20 \times 10^9/L$ ), and complications need to be collected.

### **7.8.2 Concomitant Treatment**

Throughout the study, investigators may prescribe any concomitant medications or treatments deemed necessary to provide adequate supportive care except for those listed in [Section 7.1.7](#).

Concomitant therapies are to be collected from start of screening through the end of safety follow-up period.

All concomitant medications, including all prescription, over-the-counter, herbal supplements, and IV medications and fluids will be recorded on the eCRF.

During the LTFU period until EOS, any anti-multiple myeloma treatment is to be recorded.

For all concomitant medication collect therapy name, indication, dose, unit, frequency, route, start date, and stop date.

#### **7.8.2.1 Supportive Care**

Subjects should receive supportive care according to local guidelines for blood product support, antibiotics, antivirals, analgesics, etc

Please refer to [Section 7.4.2.1.2.2](#) and [Section 7.4.2.1.2.5](#) for management of CRS and infusion related reaction.

Oxygen administration as supportive measure is permitted during study treatment.

To prevent TLS, all subjects should receive at the discretion of the investigator appropriate hydration and supportive measures (eg, rasburicase) according to local standard of care and institutional guidelines. Please refer to [Section 7.8.2.7](#) for management guidelines of TLS.

#### **7.8.2.2 Treatment of Myeloma Bone Disease, Hypercalcemia, Pain, and Renal Failure**

Treatment of myeloma bone disease, hypercalcemia, pain, and renal failure should be done according to institutional standards. This may include concurrent treatment with bisphosphonates or denosumab. Radiotherapy for palliative care such as bone pain is only permitted after discussion with Amgen medical monitor.

#### **7.8.2.3 Bone Disease Therapy**

Bisphosphonate or other therapy to mitigate myeloma bone disease and associated complications is permitted and should follow investigators' standard of care. Such therapy is ideally administered during weeks between AMG 420 infusions.

#### **7.8.2.4 Intravenous Immunoglobulin Treatment**

Intravenous immunoglobulin (IVIG) may be administered to patients per investigators' standard of care, providing this treatment commences following cycle 2 infusion of AMG 420 and is provided during weeks between AMG 420 infusions.

#### **7.8.2.5 Growth Factors**

The use of growth factors such as erythropoiesis-stimulating proteins as well as granulocyte colony stimulating factor (G-CSF) will be allowed during therapy per regional and investigator standard of care. However, growth factors are not allowed at inclusion (within 7 days of applicable screening assessment) and should be avoided, if subject's condition allows, in the first treatment cycle for better assessment of safety parameters.

#### 7.8.2.6 Infections

Prophylactic antibiotics, antifungal, and antivirals are allowed and should be given according to institutional standards. Pneumocystis prophylaxis should also be given according to institutional standards. For subjects who are considered to have an increased risk for herpes infections, prophylaxis is mandatory unless medically contraindicated. Subjects who may experience neutropenia for 7 days or longer are at a high risk for infectious complications. As appropriate, these subjects should be administered prophylactic antibacterial, antifungal, and antiviral medications. These subjects should be monitored for early signs of breakthrough infections after the initiation of antibacterial therapy to prompt additional evaluation and possible therapy modification.

Subjects presenting with evidence of active infection after the start of AMG 420 treatment should be closely monitored while being treated with AMG 420. Subjects with identified, active systemic infections requiring IV antibiotics, antivirals, or antifungals should not be dosed with AMG 420 until infection has resolved, and if being treated with an anti-infectious therapy, the course of such therapy should have been completed.

Patients who develop fever greater than 38.0°C lasting more than 1 hour or fever greater than 38.3°C of any duration during AMG 420 treatment should be promptly evaluated for infection as well as cytokine release syndrome (CRS). Workup should include evaluation for bacterial, fungal, and viral etiologies using radiographic imaging and appropriate microbiological/serologic assays, and empiric therapy should be considered using investigator's institutional standard of care approach. Guidelines for dose interruption and AMG 420 discontinuation as detailed in [Tables 7-1](#) and [7-2](#) should be followed. Investigators should consider the potential immunosuppressive effects of CRS rescue medications (eg, tocilizumab, corticosteroids) in their empiric management of fever. If patients develop febrile neutropenia (defined as ANC < 1000 10^6/L with a single temperature of > 38.3°C [101°F] or a sustained temperature of ≥ 38°C [100.4°F] for more than one hour), use of standardized guidelines for management and initial treatment of neutropenic fever (eg, Infectious Diseases Society of America Clinical Practice Guidelines, Management of Febrile Neutropaenia: ESMO Clinical Practice Guidelines) is encouraged.

